Key Secondary (Virology): Time to cessation of SARS-CoV-2 viral shedding, as measured by RT-qPCR	Time from randomization to cessation of SARS-CoV-2 viral shedding, right censored at Day 14 if the patient doesn't meet criteria		Hypothetical approach where patient censored at Day 14 if the patient doesn't meet criteria if intercurrent event prior to achieving the endpoint	Hazard ratio	Patient censored at Day 14 if the patient doesn't meet criteria if study withdrawal is prior to achieving the endpoint
Secondary (Virology): Proportion of patients positive for SARS-CoV-2 virus RNA	Patients who are positive for SARS-CoV-2 virus RNA, as measured by RT-qPCR at Day 3, Day 5, Day 7 and Day 14		While on treatment approach where the outcome measure up to point of intercurrent event will be used	Difference in proportion of patients between treatments	The outcome measure up to point of study withdrawal will be used

Table 2 Estimands (cont.)

Endpoint	Variable or Outcome Measurement	Intercurrent Events		Population-Level Summary for the Variable	Handling of Missing Data
		Treatment Withdrawal/Rescue/Concomitant Medications	Death		
Secondary (Safety): Incidence of adverse events	Patients with an adverse event			Proportion of patients for each treatment	
Secondary (Safety): Severity of adverse events	Severity of adverse events determined according to NCI CTCAE v5.0	Treatment-policy strategy approach will be taken. Patients are followed, assessed and analyzed irrespective of their completion of the planned course of the study treatment and irrespective of rescue and concomitant therapy.	Not an intercurrent event as it is the outcome measure	Proportion of patients for each treatment for each severity grade	
Secondary (Safety): Incidence of serious adverse events	Patients with a serious adverse event			Proportion of patients for each treatment	The outcome measure up to point of study withdrawal will be used (contd.)
Secondary (Safety): Change from baseline in vital signs	Vital signs, including SpO2		While on treatment approach where the outcome measure up to point of intercurrent event will be used	Means for each treatment	
Secondary (Safety): Change from baseline in targeted laboratory results	Targeted laboratory results				

Table 2 Estimands (cont.)

Endpoint	Variable or Outcome Measurement	Intercurrent Events		Population-Level Summary for the Variable	Handling of Missing Data
		Treatment Withdrawal/Rescue/Concomitant Medications	Death		

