2.2 MULTIPLICITY ADJUSTMENT

The primary and key secondary endpoints ([Figure 2](#)) will be evaluated in a hierarchical manner with multiplicity control via multistage gatekeeping under the truncated Holm multiple testing procedure ([Dmitrienko et al. 2008](#)). In Families 1 and 2 of key secondary endpoints, the same truncation parameter value of 0.7 will be applied; no truncation is applied in Family 3, since it is prioritized lowest in the hierarchy and imposes no gatekeeping restrictions on subsequent families. The truncation parameter and the relative effect sizes of the endpoints influence how power is balanced over the secondary endpoint families. Truncation parameter values close to 1 should generally be chosen when the effect sizes in high-priority endpoints are relatively large in order to maximize overall power. In other settings where the effect sizes might be smaller or mixed, a truncation parameter value closer to 0 could improve overall power. A parameter value strictly less than 1 in testing families that impose parallel gatekeeping (i.e., at least one endpoint is considered statistically significant after multiplicity adjustment in order to test the next family) is needed to achieve strong overall type I error control ([Dmitrienko et al. 2009](#)).

Under this multistage gatekeeping approach, multiplicity-adjusted p-values will reflect the gatekeeping restrictions depicted in [Figure 2](#). In particular, the adjusted p-values for all key secondary endpoints in Families 1, 2, and 3 will be no smaller than the p-value for the primary endpoint. Similarly, the smallest adjusted p-value in Family 2 (3) will be no smaller than the smallest adjusted p-value in Family 1 (2). Endpoints for which the multiplicity-adjusted p-value is greater than 0.025 will not be considered statistically significant. These endpoints and all endpoints not under multiplicity control will be considered to provide supportive information. By repeated application of Proposition 4.1 of [Dmitrienko et al. \(2008\)](#), this testing strategy ensures that the overall type I error is no greater than 2.5%.

Figure 2 Multiple Testing Procedure for Endpoints

Ordering of endpoints within a family will be based on the p-value results from the hypotheses tests of the endpoints

COVID-19=coronavirus disease 2019; RT-qPCR=reverse-transcriptase quantitative polymerase chain reaction; SARS-CoV-2=severe acute respiratory syndrome coronavirus-2.

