For time to event efficacy endpoints, once the first instance of the criteria has been met at an assessment, assessments with endpoint data present prior to the assessment that demonstrates the criteria is maintained for the required duration (either ≥ 21.5 hours or ≥ 43 hours as appropriate), must also meet the criteria to meet the endpoint i.e., subsequent assessments after a patient first meets the criteria but prior to the assessment showing maintenance of that criteria for 21.5 hours (or 43 hours if appropriate) must also meet the criteria if there is non-missing data at these assessments.

In addition, for time to event efficacy endpoints, once the endpoint has been met, subsequent data for a patient that does not meet the efficacy criteria will not result in a

null endpoint. Due to this, these endpoints can also be thought of as the time to first instance of a maintained defined criteria (such as alleviation) where maintained here refers to the required duration.

Secondary efficacy and virology endpoints that evaluate proportion of patients will be analyzed using a Cochran-Mantel-Haenszel test adjusted by the stratification factors for region (North America, Europe, ROW) and high-risk factor (yes, no), unless stated otherwise. The proportion in each treatment arm together with the difference in proportions, odds ratio and accompanying 97.5% CIs will be presented along with the p-value.

Continuous secondary virology endpoints, such as change from baseline endpoints, will be analyzed using an analysis of covariance (ANCOVA) model with region (North America, Europe, and ROW), high-risk factor (yes, no) as stratification variables, and the baseline value of the studied measure as a covariate. The least squares mean (LSM) change and its standard error (SE) of means in each group, the difference between two groups in least squares mean (LSM change), SE, and 97.5% CI, and p-values will be presented. Additionally, descriptive summaries for the change from baseline will also be presented by treatment group.

Area under the concentration curve (AUC) for secondary and exploratory endpoints will be analyzed using the van Elteren test where AUC is calculated using the trapezoidal method. AUC of change from time 0 (t_0) to time K (t_k) is given by the formula:

$$\sum_{k=1}^K \frac{(y_k + y_{k-1})(t_k - t_{k-1})}{2},$$

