5.3.2 Main Analytical Approach for Primary Endpoint(s)

The hazard ratio (HR) for TTAIS for RO7496998 (AT-527) and placebo arms will be tested using the stratified log-rank test with the following stratification factors: Region (North America, Europe, and ROW) and high-risk factor (yes, no), unless otherwise required as detailed in Section 5.1. Kaplan-Meier plots, median time to response with 97.5% CIs as estimated from the Kaplan-Meier curve, and difference in median time between treatment groups with 97.5% CIs using bootstrap method will be presented. In addition, the treatment groups will be compared descriptively using a Cox proportional hazards model adjusting for the stratification factors and a hazard ratio with a 97.5% CI will be produced.

The log-rank test is most powerful when the assumption of proportional hazards holds. The proportional hazards assumption will be tested graphically using the log-cumulative hazard plot by treatment group, where the plots for each treatment group will be parallel if the proportional hazard assumption holds. Should the proportional hazards assumption not hold, the Gehan-Wilcoxon test stratified by Region and high-risk factor will be used to analyze the data.

The primary estimand is defined in [Table 2](#). Summaries of the proportion of patients experiencing an intercurrent event and the time to the intercurrent event will be created. The WHO Drug Global B3 Format dictionary will be used for concomitant medications including rescue medication.

The statistical hypotheses for the primary endpoint is defined in Section [2.1](#).

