5.3.4 Supplementary Analyses for Primary Endpoint(s)

5.3.4.1 Subgroup Analyses for Primary Endpoint(s)

The generalizability of primary endpoint results when comparing RO7496998 (AT-527) to placebo will be investigated by estimating the treatment effect in subgroups.

Summaries of primary endpoint by the following subgroups will be provided:

- Stratification factors:
 - Region (North America, Europe, and ROW)
 - Presence of a high risk factor for hospitalization due to COVID-19 (yes, no)
- Key baseline demographics:
 - Age (Adolescent 12–<18 years, Adult <65 years, Adult \geq 65 years)
 - Sex (Female, Male)
 - Race/Ethnicity
- Disease characteristics:
 - Time from symptom onset to study treatment in days (\leq 3, $>$ 3)
 - Vaccinated for COVID-19 (Yes, No)

- Baseline viral load (high, low; based on median baseline viral load)
- Seropositive status at baseline (Yes, No)
- Presence of a high-risk factor: Obesity (Yes, No)
- Presence of a high-risk factor: Cardiovascular disease (Yes, No)
- Presence of a high-risk factor: Chronic lung disease (Yes, No)
- Presence of a high-risk factor: Chronic metabolic disease (Yes, No)
- Presence of a high-risk factor: Immunocompromised (Yes, No)
- Presence of a high-risk factor: Chronic liver disease (Yes, No)
- Presence of a high-risk factor: Chronic kidney disease (Yes, No)

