5.4.1.5 Time to Cessation of SARS-CoV-2 Viral Shedding as Measured by RT-qPCR

Time to cessation of viral shedding by RT-PCR is defined as the time from randomization to the first time when a negative qualitative virus RNA by RT-PCR test result is obtained. The same statistical methods as for the primary endpoint will be used as described in Section 5.3.2.

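### The confirmatory test of time to cessation of viral shedding is valid, but it leaves out baseline viral load and so forgoes power if load predicts clearance

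*SAP*

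**What the plan says.** SAP Table 2 lists the endpoint as "Key Secondary (Virology): Time to cessation of SARS-CoV-2 viral shedding, as measured by RT-qPCR", with censoring at Day 14 and a hazard ratio as the summary. SAP 2.2 states that the primary and key secondary endpoints "will be evaluated in a hierarchical manner with multiplicity control via multistage gatekeeping under the truncated Holm multiple testing procedure". Of the six endpoints under SAP 5.4.1, this is the only virological one.

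SAP 5.4.1.5 defines the event as "the first time when a negative qualitative virus RNA by RT-PCR test result is obtained". For the analysis it says "The same statistical methods as for the primary endpoint will be used as described in Section" 5.3.2. There the endpoint is "tested using the stratified log-rank test with the following stratification factors: Region (North America, Europe, and ROW) and high-risk factor (yes, no"). A descriptive Cox model adjusts for the same two factors, and a stratified Gehan-Wilcoxon test replaces the log-rank if proportional hazards fails.

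Baseline load appears elsewhere in the SAP:

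- Section 5.1: the ANCOVA of continuous virology endpoints includes "the baseline value of the studied measure as a covariate".
- Section 5.3.4.1: it is a subgroup factor for the primary endpoint, "Baseline viral load (high, low; based on median baseline viral load").
- Section 5.7.2.2: it is tabulated as a baseline characteristic.
- Section 5.5.2: adjustment for baseline RNA is mentioned as optional, under the exploratory virology endpoints.

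**The concern.** The event is a fall in RNA to a negative result, so the starting load should largely set how far a patient has to go. A strong prognostic factor left out of a log-rank test puts patients with very different clearance rates into the same risk sets, and the test loses sensitivity to a treatment effect. The plan adjusts for baseline in a supportive analysis of this assay but not in the one virology test that carries alpha. At stake is the chance of a confirmatory antiviral finding if the drug works. The supportive CMH tests of the proportion RNA-positive at Days 3, 5, 7 and 14 (SAP 5.4.3.2) have the same omission.

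**Working it through.** **1. The plan's own figure.** The stated power is for the primary endpoint (TTAIS) only: HR 1.25, two-sided 0.025, 90% power, 2:1 allocation (SAP 3).

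Events = (z₀.₉₈₇₅ + z₀.₉₀)² / [p(1−p)(ln HR)²] = (2.241 + 1.282)² / [(2/3)(1/3)(0.2231)²] = 12.41 / 0.01107 ≈ 1122.

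Patients = 1122 / 0.90 ≈ 1247, against the stated 1248. Both reproduce. No counterpart is given for viral shedding.

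**2. Inputs for viral shedding.**

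- From the documents: 1248 patients at 2:1 (832 and 416), swabs on Days 3, 5, 7 and 14, censoring at Day 14, two-sided 0.025 (critical value 2.241).
- Assumed: treatment HR 1.25 conditional on load (borrowed from the primary endpoint), 55% or 60% of placebo patients negative by Day 14, and the full 0.025 available.
- Varied: r, the multiplier of the clearance hazard per SD of baseline log10 load.

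Model: hazard = λ × 1.25^(treatment) × r^(standardised load), with clearance seen only at the scheduled swabs.

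**3. Check at r = 1.** With 60% of placebo negative there are about 817 events. Schoenfeld power = Φ(0.2231 × √(817 × 2/9) − 2.241) = Φ(0.765) ≈ 78%. The simulation gave 77%.

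**4. Simulated power, without → with baseline-load strata.** Six strata stand for region by risk. Load is added as quartiles (24 cells) in A and B and as quintiles (30 cells) in C.

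| r per SD | A: 60% of placebo negative | B: 55% | C: 55% |
|---|---|---|---|
| 1.0 | 77 → 77% | 68 → 68% | – |
| 0.8 | 75 → 76% | 72 → 71% | 70 → 70% |
| 0.7 | 73 → 76% | – | – |
| 0.65 | – | 66 → 70% | 66 → 71% |
| 0.6 | 64 → 72% | – | – |
| 0.5 | 59 → 71% | 54 → 66% | 56 → 68% |
| 0.4 | 49 → 69% | 48 → 66% | 49 → 66% |

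Run A used 1500 trials per row, with a Monte Carlo error of about ±2.5 points on each power. The one-point reversal in B at 0.8 is noise of that order.

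**5. Sensitivity to the assumptions.**

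- *Clearance rate.* Comparing an unstratified log-rank with one stratified by load quintile only, the gains at r = 0.65, 0.5 and 0.4 are 2, 6 and 12 points with about 39% negative by Day 14. They are 5, 11 and 18 points at 55%, and 6, 15 and 22 points at 70%.
- *Local alpha.* At an assumed 0.0125, with 55% of placebo negative and quartiles added to the six strata, power is 53 → 58%, 46 → 59% and 37 → 54% for the same three values of r.
- *Different mechanism.* Assume a linear log10 decline from a mean load of 6 to log10(60) ≈ 1.8 (the value SAP 5.1 imputes for a negative sample), with treatment speeding the decline by 12%. Power is then 90 → 95%, 77 → 92% and 63 → 87% for load SDs of 1.0, 1.5 and 2.0.

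**6. Type I error.** Null rejection was about 0.022 for both the six-stratum and the six-by-quartile test. In 4000 trials comparing an unstratified with a quintile-stratified test, it was 0.0275 and 0.0258.

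**The case against.** The planned test matches the randomisation strata, agrees with Protocol 6.4.3 and holds its level. The trial is sized on TTAIS alone, so no power is promised here and none is broken. The size of the loss rests wholly on assumptions and may be nil. Baseline load is tabulated by arm, so an imbalance would be seen, and change in RNA is already baseline-adjusted. All of this stands, and it makes the point an efficiency improvement rather than the correction of an error.

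A reader might infer that the planned hazard ratio is biased towards 1. The documents do not support that. A hazard ratio not conditioned on load is a legitimate marginal summary, and under randomisation its gap from the conditional one is largely non-collapsibility. Table 2 asks only for a hazard ratio.

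A reader might also infer that a usable baseline value exists for everyone. The swab is scheduled for all, but Protocol Appendix 1 lets a patient who declines a nasopharyngeal swab give a nasal one, while SAP 5.1 evaluates secondary virology on nasopharyngeal samples. The efficacy-evaluable set (SAP 4) admits anyone positive at any point, so some patients may be negative at baseline. For them, distance to negativity has no meaning, and SAP 5.4.1.5 gives no rule. The remedy has to cover both groups.

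The optional sentence in SAP 5.5.2 does not settle the matter, because it sits under the exploratory endpoints and commits to nothing.

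**Conclusion.** The planned analysis is valid but does not use a baseline measurement that the trial schedules for all patients and that the SAP already treats as a covariate for the same assay. The power forgone is about 0 to 2 points at r = 0.8, 4 to 5 at 0.65, 11 to 12 at 0.5 and 16 to 20 at 0.4. These figures assume a conditional HR of 1.25, 55% to 60% clearance by Day 14 and the full 0.025. Lower clearance shrinks the gain and higher clearance enlarges it. If load is not prognostic, adding it costs essentially nothing (77 → 77% and 68 → 68%).

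It would go too far to say that the test certainly loses power, or loses a particular amount. The documents give no association between load and clearance, no clearance rate and no virological effect size. Figure 2 is not reproduced in the text available, so the endpoint's family and local alpha are unknown. A smaller local alpha lowers both powers, but the gap persisted at 0.0125.

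**What to change.** Before unblinding, amend SAP 5.4.1.5 as follows:

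- Make the confirmatory test a log-rank stratified by region, high-risk factor and prespecified categories of baseline nasopharyngeal log10 RNA, for example quartiles with cut points fixed from blinded pooled data.
- Give patients without a nasopharyngeal baseline their own category, and state a rule for baseline-negative patients.
- Fix the order in which sparse strata are combined, as SAP 5.1 allows. Quartiles give 6 × 4 = 24 cells, averaging 1248 / 24 = 52 patients.
- Apply the same strata to the Gehan-Wilcoxon fallback.
- Adjust the accompanying Cox model in the same way, and label its hazard ratio as conditional on baseline load.
- Keep the present test as a sensitivity analysis.

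Add the same baseline category to the CMH tests in SAP 5.4.3.2 where counts allow, and record the change in SAP Appendix 1. The cost is a few sentences and no new data. The downsides are small: more strata to manage, and a hazard ratio that answers a conditional question.

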5.4.1.6 Proportion of Patients with All-Cause Mortality

All-cause mortality is defined as an adverse event captured within the clinical database for which there is a non-missing death date (partial date of death will be considered as a death). The statistical method is detailed in Section 5.1.

5.4.2 Supportive Secondary Efficacy Endpoint(s)

5.4.2.1 Time to Alleviation or Improvement of COVID-19 Symptoms (Items 1–12 of the COVID-19 Symptom Diary) Maintained for a Duration of 43 Hours

The time to alleviation or improvement of COVID-19 symptoms is defined as the time from randomization to the first time at which all COVID-19 symptoms from Items 1-12 of the COVID-19 Symptom Diary were either alleviated, maintained or improved for a duration of 43 hours. Alleviation, maintenance or improvement of symptoms is defined as the time when all 12 COVID-19 symptoms from Items 1-12 of the COVID-19 Symptom Diary have been assessed by the patient as follows:

- For pre-existing symptoms (i.e., symptoms that existed prior to developing COVID-19) judged by the patient to be worse at screening:
 - Improvement of at least one grade on the Likert scale from baseline if the severity at baseline is graded moderate or severe:
 - Severe to moderate, mild, or none
 - Moderate to mild or none
 - Mild to mild or none
 - None to mild or none

Note: At screening, patients will only be asked if preexisting symptoms existed (within the last 30 days) and if they were worsened by COVID-19. Patients will be asked to rate the severity at baseline that needs to improve. To avoid recall bias, patients will not be asked to rate the severity of preexisting symptoms prior to COVID-19.

- For pre-existing symptoms (i.e., symptoms that existed prior to developing COVID-19) judged by the patient NOT to be worse at screening:
 - Maintained (no worsening) baseline severity if the severity at baseline is graded moderate or severe:
 - Severe to severe, moderate, mild, or none
 - Moderate to moderate, mild or none
 - Mild to mild or none
 - None to mild or none
- For new symptoms (i.e., symptoms that develop due COVID-19 which present prior to or post baseline):
 - Alleviation of COVID-19 symptoms (i.e., a score of 0 [none] or 1 [mild] on the COVID-19 Symptom Diary):
 - Severe to mild, or none
 - Moderate to mild, or none
 - Mild to mild or none
 - None to mild or none

Where the baseline assessment for COVID-19 symptom severity is missing, the COVID-19 symptoms for a patient will be treated as new symptoms and therefore must meet the alleviation criteria even if symptoms had been identified as existing prior to developing COVID-19.

5.4.2.2 Time to alleviation of individual symptoms maintained for a duration of 21.5 hours

Time to alleviation of individual symptoms (Items 1-14 of the COVID-19 Symptom Diary) is defined separately for each symptom as the time from randomization to the point at which a score of 0 or 1 for the individual symptom is met and maintained for at least 21.5 hours in patients with a symptom score ≥ 2 at baseline. The endpoints corresponding to each of the symptoms are as follows:

- Time to alleviation of nasal congestion or runny nose
- Time to alleviation of sore throat
- Time to alleviation of cough
- Time to alleviation of shortness of breath
- Time to alleviation of muscle or body aches
- Time to alleviation of fatigue
- Time to alleviation of headache
- Time to alleviation of chills/sweats
- Time to alleviation of feeling hot or feverish

- Time to alleviation of nausea
- Time to alleviation of vomiting
- Time to alleviation of diarrhea
- Time to alleviation of sense of smell
- Time to alleviation of sense of taste

The same statistical methods as for the primary endpoint will be used as described in Section [5.3.2](#).

Where a baseline assessment for COVID-19 symptom severity is missing for an individual symptom, the patient will be excluded from the analysis.

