6.4.2 Secondary Efficacy Endpoints

The secondary efficacy endpoints for this study are as follows:

- *Time to alleviation or improvement of COVID-19 symptoms (Items 1–12 of the COVID-19 Symptom Diary) maintained for a duration of 43 hours, defined as follows:*
 - *For new symptoms: time from randomization to the alleviation of COVID-19 symptoms (i.e., a score of 0 [none] or 1 [mild] on the COVID-19 Symptom Diary)*
 - *For preexisting symptoms: time from randomization to when a patient's symptoms have been maintained or improved (Note: Improved requires at least a single category improvement from baseline on the COVID-19 Symptom Diary Likert scale.)*
- Time to alleviation of COVID-19 symptoms defined as the time from randomization to the point at which the following criterion is met and maintained for at least 21.5 hours:
 - Score of 0 or 1 for Items 1–12 of the COVID-19 Symptom Diary
- *Time to alleviation of COVID-19 symptoms defined as the time from randomization to the point at which the following criterion is met and maintained for at least 43 hours:*
 - *Score of 0 or 1 for Items 1–12 of the COVID-19 Symptom Diary*
- Time to one-category improvement of baseline presenting COVID-19 symptoms (*Items 1–12 of the COVID-19 Symptom Diary*) maintained for a duration of 21.5 hours defined as time from randomization to when the symptoms have improved by at least one category from baseline on the *COVID-19 Symptom Diary Likert scale*
- Time to alleviation of individual symptoms, defined as the time from randomization to the point at which the following criterion is met and maintained (for each individual symptom) for at least 21.5 hours:
 - Score of 0 or 1 for Items 1–14 of the COVID-19 Symptom Diary
- Proportion of patients requiring hospitalization for COVID-19

- Proportion of patients with ≥ 1 COVID-19 related medically attended visit through to study end (defined as hospitalization, ER visit, urgent care visit, physician's office visit, or telemedicine visit, with the primary reason for the visit being COVID-19) (see Section 4.5.6.3 for assessments to be done at weekly visits)
- Duration of fever (time to return to afebrile state [temperature $\leq 37.5^{\circ}\text{C}$] and remaining so for at least 21.5 hours) (see Section 6.4.1)
- Frequency of COVID-19 related complications (e.g., death, hospitalization, radiologically confirmed pneumonia, acute respiratory failure, sepsis, coagulopathy, pericarditis/myocarditis, cardiac failure)

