Appendix 2 COVID-19 Symptom Diary (Cont.)

	Same as usual 0	Less than usual 1	No sense 2
13. Rate your sense of smell since you went to bed last night.			
14. Rate your sense of taste since you went to bed last night.			

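### For smell and taste, the individual-symptom endpoint measures any departure from complete loss, because a cut-off suited to the 4-point items is applied to a 3-point scale

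*SAP*

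**What the plan says.** SAP 5.4.2.2 covers the whole diary with a single definition: "Time to alleviation of individual symptoms (Items 1-14 of the COVID-19 Symptom Diary) is defined separately for each symptom". The event is that "a score of 0 or 1 for the individual symptom is met and maintained for at least 21.5 hours in patients with a symptom score" of 2 or more at baseline. The fourteen listed endpoints include "Time to alleviation of sense of smell" and "Time to alleviation of sense of taste".

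The event half of the rule comes from Protocol 6.4.2, which reads "Score of 0 or 1 for Items 1–14 of the COVID-19 Symptom Diary"; SAP Table 1 repeats it. The baseline restriction is not in Protocol 6.4.2. It appears in SAP 5.4.2.2 and is not listed in SAP Appendix 1 among the changes to protocol-planned analyses.

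The diary itself (Protocol Appendix 4, SAP Appendix 2) has two response scales. Items 1–12 run from 0 (none) through 1 (mild) and 2 (moderate) to 3 (severe). Items 13–14 have three columns: 0 for same as usual, a middle column headed "Less than usual 1", and 2 for no sense. Protocol 4.5.6.2 acknowledges that items have either three or four response options. Neither document gives Items 13–14 an alleviation or baseline rule of their own.

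**The concern.** A cut-off between 1 and 2 has a clear meaning on the 4-point items. It separates none or mild from moderate or severe, and SAP 5.3.1 explains the alleviation rule in those terms. The 3-point items have no mild category. Their score 1 takes in every deficit short of total loss, however large, and their score 2 is the top of the scale. The same numbers therefore define a different endpoint.

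Every composite symptom endpoint uses Items 1–12 only, so this is the only defined efficacy endpoint that uses smell and taste. If its rule does not suit the scale, the trial has no pre-specified analysis of return to usual smell or taste. A reader of the results tables could also take a time to partial return as a time to normal function.

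**Working it through.** The plan states no figure for this point, so the check is to run each scale through the two cut-offs.

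**Inputs.** Event: score 0 or 1 held for at least 21.5 hours (Protocol 6.4.2; SAP Table 1; SAP 5.4.2.2). Entry: baseline score of 2 or more (SAP 5.4.2.2). Scale labels: SAP Appendix 2 and Protocol Appendix 4.

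**Enumeration.**

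| | Items 1–12 (4-point) | Items 13–14 (3-point) |
|---|---|---|
| Analysed at baseline | moderate, severe | no sense |
| Counted as event | none, mild | same as usual, less than usual |
| Abnormal at baseline, not analysed | mild | less than usual |
| Changes counted | 2→0, 2→1, 3→0, 3→1 | 2→0, 2→1 |

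**What follows for Items 13–14.**

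1. Only one baseline level qualifies, and both other levels are events. The endpoint is time to any maintained departure from complete loss.
2. A patient who goes from 2 to 1 and stays there to Day 29 is an event. If the event were score 0, the same patient would be censored at Day 29 (SAP Table 2).
3. A patient scoring 1 at baseline does not enter that item's analysis.

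**Share of endpoints affected.** 2 of 14 individual-symptom endpoints.

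**Effect of requiring score 0, complete loss at baseline.** Any run of scores at 0 lasting 21.5 hours is also a run at 0 or 1. So for each patient, time to maintained score 0 is at least as long as time to maintained score 0 or 1. The event comes at the same time, later, or not at all.

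**Effect once partial loss is admitted.** Let *E* be the events under the current rule, *E*₂ (at most *E*) the events at score 0 among the same patients, and *E*₁ the events among the *n*₁ patients with baseline score 1, so *E*₁ lies between 0 and *n*₁. The change in event count is *E*₂ − *E* + *E*₁, which lies between −*E* and +*n*₁. The documents give no baseline distribution for smell or taste, so neither the sign of this change nor the shift in the median can be computed.

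**The case against.** The strongest reply is that the plan says alleviation, not recovery, and that alleviation tolerates a residual symptom throughout. A patient left with mild cough also counts as a success, and moving from no sense to a reduced sense is a real gain. It is true that the plan never claims full recovery. The analogy still fails at the cut-off. On Items 1–12 a moderate deficit is kept apart from a mild one and does not count as alleviated. On Items 13–14 it cannot be kept apart, and the plan offers no reason for treating the two rules as equivalent.

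A second reply is that leaving out baseline score 1 is not a separate defect. That is correct. If 0 or 1 is the event, patients already there cannot be analysed, and the same filter removes baseline mild symptoms from Items 1–12. The exclusion follows from the event definition and goes away when that definition is corrected.

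Third, requiring score 0 holds two items to full normality while twelve may stay at mild. That is a genuine cost, and relabelling the present endpoint would be a defensible minimum. It would still leave return to usual sense without a pre-specified analysis.

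Finally, the same rule applies to both blinded arms, so the randomised comparison of time to at least partial return from complete loss remains valid. That stands.

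**Conclusion.** The point holds as a definition problem in two supportive secondary endpoints. For smell and taste, SAP 5.4.2.2 measures time to any departure from complete loss, in patients with complete loss only. This follows from the text and the diary labels and needs no assumption about the data. That the 4-point cut-off was carried over without adaptation is an inference, supported by the unchanged rule and the absence of any rationale for Items 13–14.

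Three stronger readings should be resisted.

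- A reader might infer that partial-loss patients are lost to the trial's analyses. They are left out only for that item. They remain in the Items 1–12 composites and in any other item where they score 2 or more.
- A reader might infer that the correction must give fewer events and longer medians. That direction is certain only for patients with complete loss at baseline, because the correction also adds patients.
- A reader might infer that trial conclusions are at risk. SAP 2.2 and 5.1 treat endpoints outside multiplicity control as supportive information, and no primary or key secondary endpoint uses Items 13–14.

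The number of patients affected cannot be stated from the documents.

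**What to change.** In SAP 5.4.2.2 and SAP Table 1, limit the present rule (event at 0 or 1, baseline 2 or more) to Items 1–12. For Items 13 and 14, define the event as score 0 maintained for at least 21.5 hours, in patients with a baseline score of 1 or more. If the change from 2 to 1 is of interest, keep it as a separate summary labelled as at least partial return from complete loss. List the change in SAP Appendix 1, together with the baseline restriction retained for Items 1–12, because Protocol 6.4.2 contains neither.

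The cost is revised wording and two derivations on data the diary already collects, made before unblinding, which is when Protocol Section 6 requires the SAP to be signed off. It is also a documented departure from the protocol's endpoint wording, or an amendment to it. The downside is a stricter criterion for these two items than for the other twelve, which a table footnote should state.
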